4.3 Supplemental Analyses

A supplemental analysis of OS will be included in which OS is analyzed using Cox regression, with treatment arm and risk strata as covariates, and will include demographic and baseline characteristics which are statistically different between treatment arms (p<0.1) for covariates specified in section 3.1. Start time will be randomization on BMT CTN 0702 and all participants randomized on 0702 will be included.

Supplemental analysis of EFS will be included.

- The first will analyze EFS using Cox regression, with treatment arm and risk strata as covariates, and will include demographic and baseline characteristics which are statistically different between treatment arms (p<0.1) for covariates specified in section 3.1. Start time will be randomization on BMT CTN 0702 and all participants randomized on 0702 will be included.
- The second will explore cause-specific hazards for each component of EFS. Cox models
 with treatment arm, risk strata, and demographic/baseline covariates as specified above
 will be used. Start time will be randomization on BMT CTN 0702 and all participants
 randomized on 0702 will be included. For each component, the other components of EFS
 will be considered censoring events.
- The third will analyze EFS using Cox regression in the subset of 0702 participants who initiated lenalidomide maintenance therapy. In this model, the outcome will be the time to

progression or death and the start time will be initiation of maintenance lenalidomide. Discontinuation of lenalidomide maintenance will be considered as a time-varying covariate. Treatment group, strata, and baseline covariates used in the first EFS regression analysis will also be included. The limited interpretation will be noted for this analysis, since it will include non-randomized comparisons and there may be bias in who enrolled in BMT CTN 07LT and continued on lenalidomide maintenance.

Supplemental landmark analyses will be included. The endpoints of PFS, OS, and EFS will be explored in the 0702-enrolled population who is alive four years post randomization (OS) or who is alive and progression- or event-free (for PFS and EFS respectively). A log rank test will compare each outcome for the groups determined by those who were taking lenalidomide at four years post randomization compared to those who were not. Kaplan meier estimates of each outcome at 5 years post randomization will be provided for each lenalidomide status group.

5. Template of Proposed Table/Figure/Listing (TFL) Shells

The templates for the Tables, Figures, and Listings are provided in the Appendix of this SAP. These templates are for illustration purposes only, and may not be the final layout or wording chosen for publications or presentations. Actual format of the tables and figures may differ and will be subject to change in the final analysis report and/or publication. Editorial changes in presentation or content will not necessarily be described in the changes to planned analyses section of the report or SAP updates.

6. References

Cox D. Regression models and lifetables (with discussion). Journal of the Royal Statistical Society 1972; Series B:187-220.

Gray RJ. A class of K-sample tests for comparing the cumulative incidence of a competing risk. Annals of Statistics 1988, 16: 1141-1154.

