### **3.3.2. Event-free Survival**

Event-free survival (EFS) time will be calculated as the time from randomization on the BMT CTN 0702 protocol until death from any cause, disease progression, or second primary malignancy, whichever comes first. Patients alive at the time of last observation or lost to follow-up will be censored at the date of last contact. Event-free survival will be compared between treatment arms once all alive patients have been followed for 5-years post randomization on the BMT CTN 0702 protocol.

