##### **Event-Free Survival**

Event-free survival (EFS) time will be calculated as the time from randomization on the BMT CTN 0702 protocol to death, progression, second primary malignancy, loss to follow-up or the end of the study, whichever comes first. Patients alive at the time of last observation or lost to follow-up will be censored at the date of last contact. The Kaplan-Meier estimate of EFS will be estimated at 5 years post randomization on the BMT CTN 0702 protocol along with corresponding 95% confidence intervals. Overall survival will be compared between treatment arms using a two-sided log-rank test once all alive patients have been followed for 5-years post randomization on the BMT CTN 0702 protocol.

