2.8.1 Changes to the planned analyses

Clarifications from the BMT CTN 07LT protocol

The protocol specified that for the primary endpoint of PFS, deaths will be counted as failures no matter when they occur. This is clarified to note that deaths that occur prior to the end of 2018 will be counted as failures and deaths that occur after progression will use time to progression rather than time to death for the primary analysis. Deaths through the end of follow-up in December 2018 will be counted, but deaths that occur between the end of BMT CTN 07LT in December 2018 and the database closure for the analysis will not be counted.

The protocol specified that for some of the secondary outcomes, the analysis would be completed once all alive patients have been followed for 5-years post randomization on the BMT CTN 0702 protocol. This is clarified to note that the secondary outcomes will be analyzed at the same time as the primary analysis -- once all alive patients have been followed for 5-years post randomization on the BMT CTN 0702 protocol or the end of 2018.

The protocol specified that a Cox model would be used to analyze PFS data, but did not require that treatment group and risk strata be included in the model. These factors will be included in the models.

Supplemental analyses of EFS and OS have been added to incorporate a Cox model analysis adjusting for baseline risk factors for the 0702-enrolled population and to incorporate a Cox model investigating EFS, baseline risk factors, and discontinuation of lenalidomide among the population that initiated maintenance therapy. Additional cause-specific analyses will show the Cox model results for each component of EFS, with censoring at the time of the other components.

Additional supplemental landmark analyses of PFS, OS, and EFS have been added to explore these outcomes between those on long term lenalidomide and those not on long term lenalidomide.

3. Participant Characteristics and Compliance

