4.1 Analysis of the Primary Endpoint

The primary analysis of PFS will include all randomized subjects from the BMT CTN 0702 protocol, classified according to their randomized treatment allocation, irrespective of treatment received [intent-to-treat]. The time to this event is the time from randomization on the BMT CTN 0702 protocol to progression, initiation of non-protocol anti-myeloma therapy (this includes lenalidomide if the dose is above 15mg), or death from any cause reported on BMT CTN 0702, BMT CTN 07LT, or to the CIBMTR. Patients will be censored at loss to follow-up or end of 2018, whichever comes first. For those lost to follow-up, if loss occurred during 0702, censoring will occur at last myeloma evaluation before loss to follow-up. For those lost to follow-up on BMT CTN 07LT, censoring will occur at the last contact date reported on the study status follow-up form. For those who completed BMT CTN 0702 but did not enroll on 07LT, censoring will occur at the last evaluation of progression provided by the CIBMTR.

The treatment arms will be compared with a two-sided log-rank test stratified on risk status. Tests will be performed pair-wise at the 0.05/3 level to maintain type I error at 0.05 for this endpoint in this analysis. A Kaplan-Meier plot of PFS and 5-year estimates of PFS will be provided by treatment group.

A secondary analysis of PFS will be conducted using Cox regression, with treatment arm and risk strata as covariates, and adjusting for demographic and baseline characteristics which are statistically different between treatment arms (p<0.1) for covariates specified in section 3.1. Start time will be randomization on BMT CTN 0702.

In another secondary analysis of PFS, discontinuation of lenalidomide maintenance will be considered as a time-varying covariate in a separate Cox regression model for those who initiated lenalidomide; in this model, the outcome will be the time to progression or death from initiation of lenalidomide. Initiation of maintenance lenalidomide on BMT CTN 0702 will be the start time for this analysis. CIBMTR data will be used to determine whether participants who discontinued study lenalidomide also discontinued commercial lenalidomide. The limited interpretation will be noted for this analysis, since it will include non-randomized comparisons and there may be bias in who enrolled in BMT CTN 07LT.

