Exhibit 07LT-4B: Multivariate Cox Regression Analysis of Progression-free Survival from Initiation of Lenalidomide (Secondary Analysis of PFS)

Maximum Likelihood Estimates and Hazard Ratios

		0		
Covariate	Point Estimate	Lower Confidence Limit	Upper Confidence Limit	Model Parameter Estimate p-value
Auto/Auto treatment arm vs Auto/Maintenance arm¹				
Auto/Auto treatment arm vs Auto/RVD arm ¹				
Auto/RVD treatment arm vs Auto/Maintenance arm ¹				
Risk strata—High risk vs Risk strata—Standard risk				
Permanent discontinuation of lenalidomide (time-dependent)				
(other adjustment factor as needed)				
(other adjustment factor as needed)				
(other adjustment factor as needed)				

¹ P-values are compared to the 0.05/3 significance level.

Figure: A forest plot for the hazard ratios and confidence intervals may also be provided.

Notes for this secondary analysis:

Model covariates:

[figure not shown]
- Treatment group
- Randomized risk strata
- Any of the factors in column 2 of the table in Section 3.1 that have a test for treatment group differences that is significant at the 0.1 level. ERC-adjudicated baseline disease response will be tested using 2 categorizations (CR or better, VGPR or better). If both are significant at the 0.1 level, the one that is more significant will be used in the model.
- No interactions
- Permanent discontinuation of lenalidomide as a time varying covariate.

- Analysis population is 0702 participants who initiated lenalidomide
- Time to PFS is calculated from start time of lenalidomide
- Proc phreg in SAS, no model selection procedure

Exhibit 07LT-5: Overall Survival

Figure template for illustration only

Overall Survival by Treatment Arm

Kaplan Meier Estimates and 98.3% Confidence Intervals

	Auto/Auto	Auto/RVD	Auto/Maint		
5-year Estimates:	XX.X (XX.X, XX.X)	XX.X (XX.X, XX.X)	XX.X (XX.X, XX.X)		

Stratified Log-Rank Test for Treatment Group Differences

[figure not shown]
Treatment Group Comparison	p-value ¹
Auto/Auto vs Auto/RVD	0.XX
Auto/Auto vs Auto/Maint	0.XX
Auto/RVD vs Auto/Maint	0.XX

¹Significance level is 0.05/3 for each pairwise comparison.

Exhibit 07LT-6: Event-Free Survival

Figure template for illustration only

Event-Free Survival by Treatment Arm

Kaplan Meier Estimates and 98.3% Confidence Intervals

	Auto/Auto	Auto/RVD	Auto/Maint		
5-year Estimates:	XX.X (XX.X, XX.X)	XX.X (XX.X, XX.X)	XX.X (XX.X, XX.X)		

Stratified Log-Rank Test for Treatment Group Differences

[figure not shown]

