Supplemental Exhibit 07LT-6B: Cause-specific Multivariate Cox Regression Analysis of the Components of Event-free Survival

Maximum Likelihood Estimates and Hazard Ratios: Event=Progression, Censoring Events=SPM, Death

	Cox model	Parameter		Hazard Rati	0
Covariate	Estimate	p-value	Point		
			Estimate	Confidence limit	Confidence limit
Auto/Auto treatment arm vs					
Auto/Maintenance arm ¹					
Auto/Auto treatment arm vs Auto/RVD					
arm ¹					
Auto/RVD treatment arm vs					
Auto/Maintenance arm ¹					
Risk strata—High risk vs					
Risk strata—Standard risk					
Permanent discontinuation of					
lenalidomide					
(other adjustment factor as needed)					
(other adjustment factor as needed)					
(other adjustment factor as needed)					

¹ P-values are compared to the 0.05/3 significance level.

Maximum Likelihood Estimates and Hazard Ratios: Event=SPM, Censoring Events=Progression, Death

	Cox model	Parameter		Hazard Rati	0
Covariate	Estimate	p-value	Point Estimate	Confidence limit	Confidence limit
Auto/Auto treatment arm vs Auto/Maintenance arm ¹					
Auto/Auto treatment arm vs Auto/RVD arm ¹					
Auto/RVD treatment arm vs Auto/Maintenance arm ¹					
Risk strata—High risk vs Risk strata—Standard risk					
Permanent discontinuation of lenalidomide					
(other adjustment factor as needed)					
(other adjustment factor as needed)	· ·				
(other adjustment factor as needed)					

¹ P-values are compared to the 0.05/3 significance level.

Maximum Likelihood Estimates and Hazard Ratios: Event=Death, Censoring Events=Progression, SPM

	Cox model	Parameter		Hazard Rati	0
Covariate	Estimate	p-value	Point		
			Estimate	Confidence limit	Confidence limit
Auto/Auto treatment arm vs Auto/Maintenance arm ¹					
Auto/Auto treatment arm vs Auto/RVD					
arm ¹					
Auto/RVD treatment arm vs					
Auto/Maintenance arm ¹					
Risk strata—High risk vs					
Risk strata—Standard risk					
Permanent discontinuation of					
lenalidomide					
(other adjustment factor as needed)					
(other adjustment factor as needed)					
(other adjustment factor as needed)					

¹ P-values are compared to the 0.05/3 significance level.

Figure: A forest plot for the hazard ratios and confidence intervals may also be provided.

Supplemental Exhibit 07LT-6C: Multivariate Cox Regression Analysis of Event-free Survival from Initiation of Lenalidomide

Maximum Likelihood Estimates and Hazard Ratios

[figure not shown]
	Cox model	Parameter		Hazard Rati	0
Covariate	Estimate	p-value	Point		

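### The third supplemental EFS model in SAP 4.3 is given an outcome of progression or death, which leaves second primary malignancy out of an analysis labelled EFS

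*SAP*

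**What the plan says.** SAP 4.3 lists three supplemental analyses of EFS. Of the last it says: "The third will analyze EFS using Cox regression in the subset of 0702 participants who initiated lenalidomide maintenance therapy". It then sets the outcome as the time to "progression or death and the start time will be initiation of maintenance lenalidomide", with lenalidomide discontinuation as a time-varying covariate.

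Two other places also call this model EFS. SAP 2.8.1 describes the addition as being "to incorporate a Cox model investigating EFS, baseline risk factors, and discontinuation of lenalidomide among the population that initiated maintenance therapy". The appendix shell is titled "Supplemental Exhibit 07LT-6C: Multivariate Cox Regression Analysis of Event-free Survival from Initiation of Lenalidomide".

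The definitions of EFS agree with one another. Protocol 3.3.2 ends EFS time at "death from any cause, disease progression, or second primary malignancy, whichever comes first". Protocol 5.4 runs it from randomization on the 0702 "protocol to death, progression, second primary malignancy, loss to follow-up or the end of the study, whichever comes first". SAP 1.5 and SAP 4.2 list the same three events.

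The PFS model from lenalidomide initiation is in SAP 4.1: "in this model, the outcome will be the time to progression or death from initiation of lenalidomide". The notes to its shell, Exhibit 07LT-4B, say: "Analysis population is 0702 participants who initiated lenalidomide".

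**The concern.** The sentence in SAP 4.3 names one endpoint and gives the event set of another. SPM is what separates EFS from PFS in the definitions, and it is the event that was dropped. The shell for Supplemental Exhibit 07LT-6C has no event list or notes, so the 4.3 sentence is the only place where this model's events are stated. A programmer who follows it would produce a table titled EFS that does not count SPM.

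The omission matters more here than it would in a model without a discontinuation term, because SPM and stopping lenalidomide are linked in the protocol. Section 4.3.2.1 provides for an SPM that leads to permanent discontinuation. Section 2.3.3 bars from 07LT lenalidomide those who developed an SPM after starting maintenance on 0702, non-melanoma skin cancer excepted. Under EFS as defined, such a participant's follow-up ends at the SPM. Under the outcome as written, the participant stays at risk and may contribute time and later events in the discontinued state. The omission therefore changes both the event count and the data behind the discontinuation hazard ratio.

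**Working it through.** No figure in the plan depends on this sentence, so the check compares texts.

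**Step 1. Compare the two models from lenalidomide initiation.**

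| Element | PFS model (SAP 4.1, Exhibit 07LT-4B) | Third EFS model (SAP 4.3, Supplemental Exhibit 07LT-6C) |
|---|---|---|
| Population | 0702 participants who started lenalidomide | Same |
| Start time | Initiation of maintenance lenalidomide | Same |
| Stated outcome | Progression or death | Progression or death |
| Time-varying covariate | Lenalidomide discontinuation | Lenalidomide discontinuation |
| Other covariates | Arm, risk strata, baseline factors imbalanced at p<0.1 | Arm, strata, baseline factors from the first EFS regression |

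The last row also coincides. SAP 3.1 selects baseline factors by imbalance between arms among all 0702 participants, a rule that does not depend on the outcome. One detail is not matched: SAP 4.1 uses CIBMTR data to check whether commercial lenalidomide was also stopped. SAP 4.3 does not mention this and gives no other rule.

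**Step 2. Ask whether the label or the sentence governs.** PFS elsewhere in the SAP (1.2.1, 1.5 and the primary analysis in 4.1) also ends at non-protocol anti-myeloma therapy (NPT), which the SAP 4.1 sentence for the initiator model leaves out.

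| Reading | Events in 07LT-4B | Events in 07LT-6C | Result |
|---|---|---|---|
| Sentence governs both | Progression, death | Progression, death | Same specification; SPM missing |
| Label governs 4.1, sentence governs 4.3 | Progression, death, NPT | Progression, death | Models differ; SPM still missing |
| Label governs both | Progression, death, NPT | Progression, death, SPM | Models differ; SPM counted |

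SPM is lost whenever the 4.3 sentence is followed. Duplication of the PFS model arises only in the first row.

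**Step 3. Look for another model that covers the gap.** The second supplemental EFS analysis fits cause-specific models for progression, SPM and death. The 07LT-6B shells carry a row for permanent lenalidomide discontinuation in each. That row is not marked time-dependent, and the 4.3 text does not list it as a covariate. The landmark EFS analysis compares lenalidomide status at four years and has no time-varying term.

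**Step 4. Size.** The number of lenalidomide initiators is not given, so the number of SPMs lost cannot be computed. For context only, Protocol 1.3 gives counts in the lenalidomide groups of two other trials, here without non-melanoma skin cancer:

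- CALGB/ECOG 100104, with the 2013 update: (9 hematologic + 10 solid)/231 = 19/231 = 8.2%.
- IFM 05-02: (13 hematologic + 10 solid)/306 = 23/306 = 7.5%.

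For those trials at their follow-up, these are ceilings on SPM as a first EFS event, because an SPM after progression would not count. They are not estimates for this trial.

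**The case against.** The strongest reply is that this is carried-over wording with obvious intent. Three places call the model EFS, and EFS is defined in SAP 1.5 and 4.2. The notes to Supplemental Exhibit 07LT-5B, an overall survival model, contain a similar slip: they refer to time to PFS. The SAP also uses progression or death loosely, since the SAP 4.1 sentence drops NPT from a model labelled PFS. The analysis is supplemental and non-randomized, and SAP 4.3 already says that its limited interpretation will be noted.

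Most of this stands, and it is why the point is minor. It does not remove the inconsistency, because the only sentence that states this model's events contradicts its label.

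A reader might draw stronger conclusions that the documents do not support:

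- That Exhibit 07LT-6C is bound to repeat 07LT-4B. This holds only if both sentences are read literally; if the PFS label governs 07LT-4B, that model counts NPT.
- That the SAP never sets lenalidomide discontinuation against SPM. The 07LT-6B shells show a discontinuation row in the SPM model, even though the 4.3 text does not specify it.
- That the shells for Exhibit 07LT-6 and Supplemental Exhibit 07LT-8, which combine progression with NPT as a first EFS event, set a conflicting EFS rule. SAP 5 says the shells are illustrative. Whether NPT is an EFS event is a separate question for clarification and not part of this error.

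**Conclusion.** The point holds as a minor specification error. The outcome stated for the third supplemental EFS model omits SPM and contradicts every definition of EFS in the two documents. Followed as written, it would leave SPM out of the only composite-EFS model to which the SAP text gives a time-varying discontinuation term.

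It would be wrong to infer that the trial's EFS comparison is compromised. The main EFS log-rank test, the EFS Cox model from randomization, the cause-specific models and the landmark EFS analysis keep SPM as an event. The primary PFS test and its alpha are not touched.

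The conclusion rests on reading the 4.3 sentence as the operative event list, since no other text or shell gives one for this model. The numerical effect cannot be computed from the documents.

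**What to change.** In SAP 4.3, state the outcome of the third EFS analysis as the first of progression, death or SPM (excluding non-melanoma skin cancer) after initiation of maintenance lenalidomide.

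In the same place, state how a participant with an SPM between randomization and lenalidomide initiation is handled. Adding SPM to the outcome makes this rule necessary, because the clock starts at initiation rather than randomization. One option is to exclude such participants from the risk set as not event-free at time zero. That would match the landmark EFS analysis in SAP 4.3, which requires participants to be event-free at its starting point.

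The cost is about two sentences in SAP 4.3. A matching event note under Supplemental Exhibit 07LT-6C would help. No new data are needed: SPM is already collected from randomization for the SPM and EFS endpoints, and the lenalidomide start date is already the time origin of the SAP 4.1 model.

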#### **2.3.3. Patient Exclusion Criteria for Long-term Lenalidomide Maintenance Therapy**

Patients who meet any of the following criteria will be ineligible to receive long-term lenalidomide maintenance therapy as part of this study\*:

1. Patients who have evidence of disease progression prior to enrollment (see Section 3.1 for disease progression definition).

---

\* All patients will be followed for long-term outcomes.

2. Patients who were discontinued from BMT CTN 0702 lenalidomide maintenance therapy, for any reason, prior to the completion of the 3 years of 0702 maintenance.
3. Female patients who are pregnant (positive -BetaHCG) or breastfeeding.
4. Females of childbearing potential (FCBP) or men who have sexual contact with FCBP unwilling to use contraceptive techniques (Appendix B) during the length of lenalidomide maintenance therapy.
5. Patients who experienced thromboembolic events while on full anticoagulation during prior therapy with lenalidomide.
6. Patients unwilling to take DVT prophylaxis.
7. Patients who developed a second primary malignancy, excluding non-melanoma skin cancers after initiation of lenalidomide maintenance therapy on BMT CTN 0702.

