## 2.4. Study Treatments

### 2.4.1. Lenalidomide

Lenalidomide will be administered initially at the patient's last documented dose prior to discontinuation of BMT CTN 0702 lenalidomide maintenance therapy. Cycle duration is 28 days. Patients will continue lenalidomide until disease progression, or discontinuation due to toxicity, death, or withdrawal from the study. Patients who discontinue lenalidomide due to any reason other than death, or withdrawal of consent will continue to be followed per Section 4.4.1

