			Estimate	Confidence limit	Confidence limit
Auto/Auto treatment arm vs					
Auto/Maintenance arm ¹					
Auto/Auto treatment arm vs Auto/RVD					
arm ¹					
Auto/RVD treatment arm vs					
Auto/Maintenance arm ¹					
Risk strata—High risk vs					
Risk strata—Standard risk					
Permanent discontinuation of					
lenalidomide					
(other adjustment factor as needed)					
(other adjustment factor as needed)					
(other adjustment factor as needed)					

[figure not shown]
¹ P-values are compared to the 0.05/3 significance level.

Figure: A forest plot for the hazard ratios and confidence intervals may also be provided.

Supplemental Exhibit 07LT-6: Landmark Analysis of PFS

Figure template for illustration only

Kaplan Meier Estimates and 95% Confidence Intervals

	Lenalidomide taken at 4 years post randomization	Lenalidomide not taken at 4 years post randomization
5-year Estimates:	XX.X (XX.X, XX.X)	XX.X (XX.X, XX.X)

Log-Rank Test for Group Differences

[figure not shown]
Comparison	N	Total Number with an Event	p-value ¹
Lenalidomide use at 4 years			
Yes	xxx	XXX	
No	xxx	XXX	0.XX

¹Significance level is 0.05.

Supplemental Exhibit 07LT-7: Landmark Analysis of OS

Figure template for illustration only

Overall Survival by 4-Year Lenalidomide Status

Kaplan Meier Estimates and 95% Confidence Intervals

	Lenalidomide taken at 4 years post randomization	Lenalidomide not taken at 4 years post randomization		
5-year Estimates:	XX.X (XX.X, XX.X)	XX.X (XX.X, XX.X)		

Log-Rank Test for Group Differences

[figure not shown]
Comparison	N	Total Number with an Event	p-value ¹
Lenalidomide use at 4 years			
Yes	xxx	XXX	
No	XXX	XXX	0.XX

¹Significance level is 0.05.

Supplemental Exhibit 07LT-8: Landmark Analysis of EFS

Figure template for illustration only

Event-Free Survival by 4-Year Lenalidomide Status

Kaplan Meier Estimates and 95% Confidence Intervals

	Lenalidomide taken at 4 years post randomization	Lenalidomide not taken at 4 years post randomization		
5-year Estimates:	XX.X (XX.X, XX.X)	XX.X (XX.X, XX.X)		

Log-Rank Test for Group Differences

			First Event			
Comparison	N	Total Number with an Event	PRG or NPT	SPM	ртн	p-value ¹
Lenalidomide use at 4 years						
Yes	XXX	XXX	XXX	XXX	XXX	
No	XXX	XXX	XXX	XXX	XXX	0.XX

¹Significance level is 0.05.

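### The 4-year overall survival landmark by lenalidomide use keeps progressed patients and is unstratified, so it is confounded by progression status; the documents do not fix the size of the bias.

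*SAP*

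**What the plan says.** SAP 2.8.1 gives the purpose: "Additional supplemental landmark analyses of PFS, OS, and EFS have been added to explore these outcomes between those on long term lenalidomide". The other group is patients off the drug.

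SAP 4.3 sets the populations as patients "who is alive four years post randomization (OS) or who is alive and progression- or event-free (for PFS and EFS respectively"). The PFS and EFS sets thus exclude earlier progression, while the OS set is everyone alive at 4 years. On the test: "A log rank test will compare each outcome for the groups determined by those who were taking lenalidomide at four years post randomization". The comparison group is everyone else in the set. No stratification or covariate is mentioned.

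The shell agrees. "Supplemental Exhibit 07LT-7: Landmark Analysis of OS" carries the title "Log-Rank Test for Group Differences", a 0.05 significance level and 5-year estimates with 95% limits. The arm comparisons of OS and EFS in Exhibits 07LT-5 and 07LT-6 are labelled as stratified.

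On treatment, Protocol 2.4.1 (repeated in SAP 1.4) says: "Patients will continue lenalidomide until disease progression, or discontinuation due to toxicity, death, or withdrawal from the study". Protocol 2.3.3 excludes from 07LT lenalidomide "Patients who have evidence of disease progression prior to enrollment" and also "Patients who were discontinued from BMT CTN 0702 lenalidomide maintenance therapy, for any reason, prior to the completion of the 3 years of 0702 maintenance". Patients with a second primary malignancy after starting maintenance are excluded too.

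The landmark text does not define taking lenalidomide. SAP 1.2.2 expects some commercial use. The rules on commercial use in SAP 4.1 and Supplemental Exhibit 07LT-3 concern discontinuation outputs only.

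**The concern.** A landmark at 4 years avoids immortal-time bias but not confounding by what happened before the landmark. In the PFS and EFS versions, prior progression is removed by design. In the OS version it stays in, and the treatment rules push progressed patients into the not-taking group. The two groups can then differ in survival only because one holds more patients with progressed disease.

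The exhibit would print 5-year OS by lenalidomide status with a p-value judged against 0.05, and a reader would naturally take this as evidence on long-term lenalidomide. The SAP attaches its limited-interpretation note to the discontinuation Cox models for PFS (SAP 4.1) and EFS (SAP 4.3), not to the landmarks. SAP 2.8 plans no sensitivity analyses that might expose the problem.

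**Working it through.** **The plan's own figure.** The documents give no sample size, event count or effect for this landmark. The one size calculation reproduces: 758 × 0.55 = 416.9, rounded up to 417; 758 × 0.75 = 568.5, rounded up to 569 (SAP 2.1). The 758 patients and the 55-75% range for 3-year PFS are used below.

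**How many survivors have progressed.** In the cited maintenance trial of Protocol 1.2 with 4-year PFS 43% and OS 73% on lenalidomide, (73 − 43)/73 = 41% of those alive at 4 years had progressed. For 0702, constant hazards give 4-year PFS of 0.55^(4/3) = 45.1% or 0.75^(4/3) = 68.1%. If 4-year OS is 80% (assumed; the other cited trial reports 80% at 48 months' median follow-up), the progressed share is 44% or 15%.

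**Mortality after progression.** Protocol 1.2 gives medians of 29 and 48 months. Hazard = 12 ln 2 / median = 0.287 or 0.173 a year.

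**Direction.** Let q be the progressed share at 4 years, *a* the share of progression-free patients taking lenalidomide, and *b* the share of progressed patients taking it. The progressed fraction is

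- among takers: qb / [qb + (1 − q)a]
- among non-takers: q(1 − b) / [q(1 − b) + (1 − q)(1 − a)]

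The first is below the second exactly when b < a. Proportions matter, not counts: with 606 patients (0.80 × 758), q = 0.2, a = 0.4 and b = 0.6, there are 606 × 0.2 × 0.6 = 73 progressed takers and 606 × 0.8 × 0.4 = 194 progression-free takers, yet the simulated null HR is 1.34, against lenalidomide.

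**One case by hand, no drug effect.** Take q = 0.30, a = 0.6 and a 29-month median. Assume non-progression death at 1.5% and new progression at 15% a year. One-year survival from the landmark is exp(−0.287) = 0.751 if progressed. If progression-free it is exp(−0.165) + [0.15/(0.165 − 0.287)] × [exp(−0.287) − exp(−0.165)] = 0.968.

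| b | Progressed fraction, taking / not | 5-year OS, taking / not |
|---|---|---|
| 0 | 0 / 0.517 | 96.8% / 85.5% |
| 0.2 | 0.125 / 0.462 | 94.1% / 86.7% |
| 0.6 (= a) | 0.30 / 0.30 | 90.3% / 90.3% |
| 0.8 | 0.364 / 0.176 | 88.9% / 92.9% |

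**Null simulation.** 758 patients, exponential times, 3-year PFS 55/75%, post-progression median 29/48 months, a = 30/50/70%, follow-up uniform over 1-3 years after the landmark, two-sided 0.05 (the exhibit does not state sidedness). Ranges run over these settings.

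| Progressed patients taking | Non-progression death a year | HR | Rejection |
|---|---|---|---|
| 0% | 1% | 0.23-0.36 | 79-100% |
| 0% | 2% | 0.28-0.47 | 59-100% |
| 0% | 3% | 0.33-0.57 | 43-100% |
| 10% | 1% | 0.30-0.61 | 41-100% |
| 20% | 1% | 0.38-0.83 | 12-99% |
| equal shares | 1% | 0.99-1.03 | 3-7% |
| 70%, against 50% of progression-free | 1% | 1.35-1.53 | – |

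At 20% progressed use and 3% a year, the lowest rejection rate is 6%.

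**After stratifying by progression at 4 years.** At 1% a year, HR 0.96-1.04 and rejection 3-7%. Restricting to progression-free patients gives HR 0.94-1.06 and rejection 3-8%. Both assume that use is random within strata. If progression-free non-takers die without progression at 2 or 3 times the rate of takers, the restricted null HR is still 0.69-0.88 or 0.52-0.77.

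**The case against.** The strongest reply is that these landmarks are supplemental, added to explore, non-randomised, and feed no decision. The SAP already recognises this kind of bias in its discontinuation models, so a definition and a caveat might be enough. That stands as a limit on priority. It does not remove the point, because the note is not attached to the landmarks and the PFS and EFS versions already apply the restriction that OS lacks.

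A second reply is that the size is assumed. This also stands. Neither share is in the documents, nor is the non-progression death rate, and moving that rate from 1% to 3% a year raises the upper end of the null HR from 0.36 to 0.57 when no progressed patient is on drug. A reader might infer that the exhibit must show a large spurious benefit. The documents do not support that: if post-progression or commercial lenalidomide counts as taking, the bias can shrink, vanish or reverse.

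Third, stratification does not make this a drug comparison. Stopping for toxicity or second malignancy is not random, and the 07LT exclusions reinforce it. This stands, and it is why the note is needed as well.

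A reader might also count Supplemental Exhibit 07LT-5B as support. It models OS with time-dependent discontinuation, has no matching text in SAP 4.3, and carries a note about time to PFS. SAP 5 calls the templates illustrative, so this is a separate item to reconcile and says nothing about the landmark.

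**Conclusion.** The concern holds in this form: the OS landmark is confounded by progression status. Given higher mortality after progression, which the cited medians support, it favours lenalidomide under no drug effect whenever a smaller proportion of progressed than of progression-free patients counts as taking it. The stop-at-progression rule makes that pattern likely but does not guarantee it.

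The size is not determined by the documents. With no progressed use, 30-70% progression-free use and 1-3% a year non-progression death, the null HR is about 0.23-0.57 and rejection about 43-100%. At 20% progressed use, rejection ranges from near nominal to almost certain. These figures rest on constant hazards, the protocol's 3-year PFS range and the 29- and 48-month medians.

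It would be wrong to infer any threat to the primary PFS analysis or to the randomised OS comparison; neither uses lenalidomide status. This should be fixed, at low priority.

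**What to change.** 1. In SAP 4.3 and Supplemental Exhibit 07LT-7, stratify the OS log-rank by progression status at 4 years, and show Kaplan-Meier curves and the HR within each stratum. Alternatively, restrict to progression-free patients, as the PFS landmark does. The usual baseline risk strata would not serve, because the confounder arises after randomisation.
   - Build the stratum from progression and non-protocol therapy other than lenalidomide, not from the raw PFS event flag. SAP 4.1 counts lenalidomide above 15 mg as non-protocol therapy, so the raw flag could put a progression-free patient in the progressed stratum because of the exposure under study.
   - State a rule for patients alive at 4 years whose progression follow-up ended earlier; under SAP 4.1 and 4.2, PFS and OS are censored at different dates. One option is last known status, with the number of such patients reported.
2. Define taking lenalidomide at 4 years: whether study, commercial and post-progression use count, and within what date window. Tabulate the share taking in each stratum, since the two shares set the direction of the unstratified bias and much of its size.
3. Attach the limited-interpretation note to the landmark exhibits, naming non-random stopping for toxicity or second malignancy.

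The cost is SAP wording, two definitions, a stratum variable from data already planned, and some precision. Expected deaths are about 23-44 among progression-free patients against about 66-127 among all alive at 4 years (1-3% a year non-progression death). At 1% a year the 95% interval is roughly the HR multiplied and divided by 1.4-1.8 unstratified, and by 2.0-2.5 if restricted. With 10-20% progressed use, the progressed stratum supplies 38-72% of the information in the pooled stratified HR, hence the display by stratum. Residual confounding within strata remains.
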